### 6.5.2 *Determination of Sample Size*

Sample size calculations were based on the primary endpoint under the following assumptions and operating characteristics: a) 73% angiographic occlusion at the 12-18 month visit in patients receiving smaller coils (control arm); b) a 9% absolute improvement (to 82%) in the incidence of angiographic occlusion in patients receiving larger coils; c) Approximately 80% power on a two-sided proportion test; and d) a significance level of 0.05. A sample size of 650 (325 in each arm) will allow us to detect the specified effect size with adequate power. Sample size was calculated using the `power.prop.test` function in R (R Core Team 2021).

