### 6.5.3 *Missing Primary Endpoint Data*

Patients without previous evidence of inadequate angiographic occlusion, either on the 3 to 6 month visit angiogram or on a clinically driven angiogram taken prior to study exit, that miss the 12 to 18 month angiogram, or whose 12 to 18 month angiogram is not readable by the core lab, will be missing the primary endpoint. Patients missing the primary endpoint who die prior to or during the 12 to 18 month visit window (up to 18 months post-randomization) and die with known cause of death related to their aneurysm or unknown cause of death will be considered treatment failures with inadequate occlusion. Patients missing the primary endpoint with a known cause of death unrelated to their aneurysm will be considered missing.

Patients with missing primary endpoint data will have their 12 to 18 month angiographic

occlusion status imputed via multiple imputation assuming that the data are missing at random. The imputation model will be stratified by randomization assignment and include age, sex, randomization strata for aneurysm status, randomization strata for wide neck status, aneurysm size, and angiographic occlusion status at the 3 to 6 month visit. Since this model includes a mixture of variables types (i.e. continuous and binary), a fully conditional specification method will be used (Berglund 2014).

The main feature of the imputation approach is the creation of a set of clinically reasonable imputations for angiographic occlusion for each patient with missing data. This will be accomplished using a set of repeated imputations created by predictive models based on the majority of participants with complete data. The imputation models will reflect uncertainty in the modeling process and inherent variability in patient outcomes, as reflected in the complete data. Thirty datasets will be imputed.

After the imputations are completed, all of the data (complete and imputed) will be combined and the analysis performed for each imputed-and-completed dataset. Rubin's method of multiple (i.e., repeated) imputation will be used to estimate treatment effect (Rubin 1986).

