#### **6.5.4 *Multicenter Studies***

The trial will be conducted in up to 25 clinical centers. Data will be pooled across all clinical centers. A sensitivity analysis of the primary endpoint will be conducted using a mixed effect log-binomial regression model with center as a random effect.

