#### **6.5.6 *Examination of Subgroups***

Subgroup analyses of the primary endpoint will be performed for key clinical subgroups, classified at baseline. Pre-defined subgroups include:

- Aneurysm status (recently ruptured (within 15 days) vs. not recently ruptured)
- Dome to neck ratio (not wide neck vs. wide neck)
- Aneurysm location (anterior vs posterior circulation)
- Age (<65, vs. ≥65)
- Sex (male vs. female)
- Race (American Indian or Alaska Native, Asian, Black or African American, Native Hawaiian or Other Pacific Island, and White)
- Ethnicity (Hispanic vs. non-Hispanic)
- Presence of co-morbidities
  - Diabetes (yes vs. no)
  - Obesity (BMI ≥ 30 vs. BMI <30)
  - Smoking status (current, previous (>6 months), never)
- Aneurysm shape (regular vs. irregular/multilobulated)

With the exception of severity of aneurysm status and wide neck status, for which formal interaction terms will be tested, these analyses will be descriptive and conducted to explore the effect of the treatment within the subgroups. Risk ratios with their respective 95% confidence intervals will be reported within each strata. Strata that contain less than 20% of the sample size and/or in which the number of patients assigned to a specific group is less than 20 will not be considered.

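### The primary-endpoint imputation model omits seven of the eleven planned subgroup variables, so those descriptive subgroup contrasts are modestly pulled toward the overall result if imputed data are used

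*Combined protocol and SAP*

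**What the plan says.** SAP 6.5.3 handles a missing primary endpoint by multiple imputation under missing at random, with thirty datasets. "The imputation model will be stratified by randomization assignment and include age, sex, randomization strata for aneurysm status". The remaining predictors are wide-neck status, aneurysm size and occlusion at 3-6 months. After imputation, observed and imputed values are pooled and analysed together.

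SAP 6.5.6 plans primary-endpoint risk ratios with 95% confidence intervals within strata of eleven variables. Four are in the imputation model: aneurysm status, neck, age and sex. Seven are not: location (listed as "Aneurysm location (anterior vs posterior circulation"), shape, smoking, diabetes, obesity, race and ethnicity. Interaction terms are tested only for aneurysm status and neck; the other analyses are descriptive. A stratum is not considered if it holds under 20% of the sample or if a group within it has fewer than 20 patients.

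SAP 4 requires the ITT population for every effectiveness analysis. SAP 6.5.6 does not say whether the subgroup analyses use imputed or observed outcomes.

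**The concern.** Given the variables in the model, an imputed outcome carries no information about a variable left out of it. Each imputed patient in an omitted-variable stratum receives a draw centred on what similar patients in the whole arm did, not on what that stratum did. The treatment contrast between strata therefore moves toward the overall effect.

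SAP 6.5.6 gives exploring the effect within subgroups as the purpose of these analyses, and this bias works against that purpose. A forest plot could look more uniform than the data are, and a reader could take that uniformity as evidence of a consistent effect. Location shows the problem. Protocol 5.5 leaves it out of stratification on the view that it does not contribute to recurrence, and an imputation model without location builds that view into the imputed outcomes.

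**Working it through.** **Inputs from SAP 6.5.2.** "73% angiographic occlusion at the 12-18 month visit in patients receiving smaller coils (control arm"; "a 9% absolute improvement (to 82%) in the incidence of angiographic occlusion"; "Approximately 80% power on a two-sided proportion test"; "a significance level of 0.05"; "A sample size of 650 (325 in each arm".

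**The plan's own figure (context only).** The pooled-variance normal approximation gives z = [0.09 × √325 − 1.96 × √(2 × 0.775 × 0.225)] / √(0.73 × 0.27 + 0.82 × 0.18) = 0.79, so power is 78.6%. That agrees with the stated approximate 80%. The point here does not depend on it.

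**Assumptions, because the documents give none of these.** Final angiograms are missing for m = 10, 20 or 30%, independently of outcome and covariates. An omitted variable splits patients 50/50. Control occlusion is 73% in both strata, and larger-coil occlusion is 91% in one and 73% in the other, so the arm mean is 82%. The true risk ratios are 0.91/0.73 = 1.247 and 0.73/0.73 = 1.000.

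**Case A: 3-6 month status unknown.** Analysed rate = (1 − m) × stratum rate + m × arm mean. At m = 0.2 the larger-coil rates are 0.8 × 0.91 + 0.2 × 0.82 = 0.892 and 0.8 × 0.73 + 0.2 × 0.82 = 0.748. Contrast kept = ln(0.892/0.748) / ln(0.91/0.73) = 80%.

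**Case B: 3-6 month status known, half of failures already seen then (assumed).** Under SAP 5.1 an early failure is a final failure, so only patients without one are imputed. With stratum rate p and arm mean P, analysed rate = (1 − m) × p + m × (1 + p) × P/(1 + P). At m = 0.2 the rates are 0.900 and 0.740. Contrast kept = ln(0.900/0.740) / ln(0.91/0.73) = 89%.

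| Missing | Case A: risk ratios | Kept | Case B: risk ratios | Kept |
|---|---|---|---|---|
| 10% | 1.234, 1.012 | 90% | 1.240, 1.007 | 94% |
| 20% | 1.222, 1.025 | 80% | 1.233, 1.014 | 89% |
| 30% | 1.210, 1.037 | 70% | 1.226, 1.020 | 83% |

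**Simulation.** Settings were 650 patients, 25 centers, 250 replicates, 5 imputations, and logistic imputation within arm on the SAP covariates. Contrast kept was 91/79/70% in case A and 94/89/84% in case B. Adding the omitted variable to the arm-specific model brought this to 98-101%. The overall risk ratio was 1.13 in every run.

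**A smaller stratum that passes the 20% rule.** Take 30% of patients, with 64% versus 84% occlusion and arm means of 73% and 82%. The true risk ratio is 0.84/0.64 = 1.31. At 10/20/30% missing it becomes 1.29/1.27/1.25 in case A and 1.30/1.29/1.28 in case B. For example, case A at 20% is (0.8 × 0.84 + 0.2 × 0.82) / (0.8 × 0.64 + 0.2 × 0.73) = 0.836/0.658 = 1.27.

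**The case against.** **The premise is inferred.** SAP 6.5.6 never says that imputed data feed the subgroup analyses. This stands as a caveat. However, the ITT rule and the absence of any other method make it the natural reading, and if the sponsor means otherwise the SAP should say so.

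**The shift is small beside sampling error.** The 30% stratum has 0.3 × 325 = 97.5 patients per arm. The standard error of the log risk ratio is √(0.16/(0.84 × 97.5) + 0.36/(0.64 × 97.5)) = 0.088, which gives a 95% interval of about 1.10 to 1.56. At 20% missing the shift is 0.2 to 0.4 standard errors. This stands and keeps the point minor. It does not remove it, because the bias runs in one direction across all seven variables.

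**Small strata drop out.** A posterior-circulation group below 20% of the sample would not be considered, and several race, ethnicity and comorbidity strata may go the same way. This stands; only strata that pass the rule matter.

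**A richer model has little to learn from.** Early failures are failures by definition and say nothing about the added terms. With half of failures late and 20% missing, the informative failures are 325 × 0.18 × 0.5 × 0.8 = 23 in the larger-coil arm and 325 × 0.27 × 0.5 × 0.8 = 35 in the control arm. Adding location, shape, smoking, diabetes and obesity together would bring the model to about 12 parameters. This stands against adding everything at once.

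**Center.** Center is also absent from the imputation model, and SAP 6.5.4 plans a "mixed effect log-binomial regression model with center as a random effect". A reader might infer that this sensitivity analysis is bound to agree with the primary result, or that reported center differences would be understated. The documents do not support either. No between-center variance or center comparison is a planned output. The SAP says randomization is stratified by site, so the treatment risk ratio should change little with or without center.

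**Conclusion.** The point holds as a minor one. Seven of eleven subgroup variables are missing from the imputation model. If the imputed datasets are used for SAP 6.5.6, descriptive contrasts on those seven shrink modestly: about 94/89/84% is kept at 10/20/30% missing with 3-6 month status known, and 91/79/70% without it. These figures rest on assumed missing fractions, an assumed even split of early and late failures, missingness unrelated to outcome or covariates, and a hypothetical subgroup effect.

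A reader might take the shrinkage to equal the missing share. That is the upper case, reached only when no patient who needs imputation has 3-6 month information.

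A reader might also infer that the primary result is distorted. Nothing here shows that: the overall risk ratio did not move in simulation. The tested interactions with aneurysm status and wide neck use variables already in a model fitted by arm, so they should be largely preserved, although those two interactions were not themselves simulated.

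**What to change.** State in SAP 6.5.6 which data the subgroup analyses use. For each subgroup variable whose strata meet the 20% rule, add that variable to the arm-specific imputation model of 6.5.3 when running its own analysis. This adds one or two parameters at a time, with sparse levels pooled. If a single enlarged model is preferred, start with location and shape. Because the model is fitted separately by arm, a main effect is enough to preserve a treatment-by-subgroup difference.

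Report an observed-data version alongside. Treat it as a check and not as the better estimate: it keeps early failures but drops patients without one who miss the final angiogram, so it leans toward failure.

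The cost is a short SAP revision, which the SAP's purpose statement allows before data lock, and some extra programming. Subgroup intervals will be slightly wider, and the added terms will rest on few late failures per arm. The primary analysis and the center sensitivity analysis need no change on this account.

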#### 5. STUDY ENDPOINTS

##### **5.1 Primary Endpoint**

The primary endpoint is angiographic occlusion at 12 to 18 months post-randomization as measured by a Raymond score of 1 or 2 (adequate occlusion). Patients' angiograms for the 3 to 6 month visit, the 12 to 18 month visit, and any clinically driven angiogram taken prior to 18 months post-randomization or study exit will be considered for angiographic occlusion. If any of these angiograms show inadequate angiographic occlusion (Raymond score >2), the patient will be considered to have inadequate occlusion at the 12 to 18 month visit and be considered a treatment failure.

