### **6.6.3 *Modified Rankin Scale***

The number and percentage of patients in each mRS score category will be reported at the 3 to 6 month and the 12 to 18 month visits by group. For each visit, a Cochran-Mantel-Haenszel “shift” analysis (also known as van Elteren's test, Savitz 2007) will be used to evaluate differences in the mRS distribution between groups. The distribution of mRS

scores is expected to differ by aneurysm status. Analyses will be repeated separately by randomization strata for aneurysm status (recently ruptured vs. not recently ruptured).

Patients with missing mRS data at the 3 to 6 and/or 12 to 18 month visit will have their data imputed via multiple imputation assuming that the data are missing at random. The imputation model will be stratified by randomization assignment and aneurysm status and include age, sex, randomization strata for wide neck status, aneurysm size, and baseline mRS. Since this model includes a mixture of variables types (i.e. continuous, binary and ordinal), a fully conditional specification method will be used (Berglund 2014). Thirty datasets will be imputed and Rubin's methods will be used to combine them and estimate treatment effect (Rubin 1986).

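### In the primary imputation model (SAP 6.5.3) the 3-6 month occlusion term, read as binary, cannot separate Raymond 1 from Raymond 2 among the patients being imputed

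*Combined protocol and SAP*

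**What the plan says.** SAP 5.1 counts Raymond 1 and 2 together as adequate occlusion and applies a rule across all scans: "If any of these angiograms show inadequate angiographic occlusion (Raymond score >2), the patient will be considered to have inadequate occlusion". The 3-6 month scan is one of those scans.

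SAP 6.5.3 then limits who can be missing the endpoint: "Patients without previous evidence of inadequate angiographic occlusion, either on the 3 to 6 month visit angiogram or on a clinically driven angiogram", who miss the 12-18 month scan or whose scan cannot be read. Aneurysm-related deaths and deaths of unknown cause become failures. Deaths known to be unrelated stay missing and are imputed.

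On the model: "The imputation model will be stratified by randomization assignment and include age, sex, randomization strata for aneurysm status", followed by the wide-neck stratum, "aneurysm size, and angiographic occlusion status at the 3 to 6 month visit". On variable types: "Since this model includes a mixture of variables types (i.e. continuous and binary), a fully conditional specification method will be used". The model for the modified Rankin Scale in SAP 6.6.3 is described differently: "Since this model includes a mixture of variables types (i.e. continuous, binary and ordinal".

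The finer reading is available. Protocol 6.2.1 has the core lab assess the degree of occlusion at the end of treatment and at follow-up. Protocol 9.1 defines recanalization as a rise in the Raymond Scale, which needs a grade at each time.

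**The concern.** Multiple imputation is valid here if, given the listed predictors, missingness is unrelated to the unseen outcome. The most informative predictor should be how the aneurysm looked at 3-6 months. Among patients who need imputation and have that scan, the listed term takes a single value. Two patients with the same baseline factors, one Raymond 1 and one Raymond 2 (usually read as complete occlusion and neck remnant), get the same imputed success probability.

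If patients with one of these grades return less often for the last scan, and the grade predicts the later result, the missing-at-random assumption fails on a variable that the trial already holds. Investigators are not blinded (SAP 3.1.2), so the return pattern could differ by arm. SAP 6.5.3 plans no analysis under departures from missing at random.

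**Working it through.** The plan gives no figure for missing endpoint data, so none can be reproduced. The sample-size figure in SAP 6.5.2 (325 per arm, 73% against 82%, two-sided 0.05) gives 78.6% power by the pooled formula, in line with the approximate 80% stated. It serves below only as a yardstick: the design effect is 9 points.

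**Step 1. Who is imputed** (SAP 5.1 and 6.5.3, no clinically driven scan above Raymond 2, deaths set aside)

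| 3-6 month scan | 12-18 month scan | Status | 3-6 month term |
|---|---|---|---|
| Raymond 1 | missing | imputed | adequate |
| Raymond 2 | missing | imputed | adequate |
| Raymond 3 | any or missing | failure by rule | inadequate |
| none or unreadable | missing | imputed | itself missing |
| none, 1 or 2 | observed | as observed | not needed |

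Rows 1 and 2 share one code. Row 3 is never imputed.

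**Step 2. Coding.** The SAP does not state how the 3-6 month variable is coded. Binary is inferred from the two-way definition in 5.1 and from the type list in 6.5.3, which omits ordinal where 6.6.3 includes it.

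**Step 3. Size.** All inputs are assumptions; none is in the documents.
- Grades 1/2/3 at 3-6 months: control 55/30/15%, larger coil 68/22/10%.
- Later adequacy: q1 = 95% after grade 1, q2 = 70% after grade 2.
- True rates: control 0.55×0.95 + 0.30×0.70 = 73.25%; larger coil 0.68×0.95 + 0.22×0.70 = 80.00%. The contrast is 6.75 points.

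Ignoring baseline covariates, the bias in an arm is M × (q1 − q2) × (s_obs − s_mis). M is the share of the arm that is missing. s_obs and s_mis are the grade 1 shares among adequate patients with an observed and with a missing later outcome.

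| Arm | Missing in grade 1 / 2 | M | s_obs | s_mis | Bias (points) |
|---|---|---|---|---|---|
| Control | 30% / 10% | 0.195 | 0.385/0.655 = 0.588 | 0.165/0.195 = 0.846 | −1.26 |
| Larger | 30% / 10% | 0.226 | 0.476/0.674 = 0.706 | 0.204/0.226 = 0.903 | −1.11 |
| Control | 10% / 30% | 0.145 | 0.495/0.705 = 0.702 | 0.055/0.145 = 0.379 | +1.17 |
| Larger | 10% / 30% | 0.134 | 0.612/0.766 = 0.799 | 0.068/0.134 = 0.507 | +0.98 |

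Bias in the contrast (larger minus control):
- Same pattern in both arms: −1.11 + 1.26 = +0.15, or 0.98 − 1.17 = −0.19.
- Opposite patterns: −1.11 − 1.17 = −2.28, or 0.98 + 1.26 = +2.24.
- Opposite but milder (20%/10% against 10%/20%): about 1.1.
- Missingness unrelated to grade: s_obs = s_mis, so zero.
- With q2 = 80%, multiply by 0.15/0.25 = 0.6: opposite patterns give 1.3 to 1.4 points, the milder ones about 0.6.

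A second assumed set lets q2 differ by arm: control 50/38/12% with q2 = 65%, larger coil 65/27/8% with q2 = 70%. The true contrast is 8.45 points. The same pattern in both arms gives 8.0 (10%/30%) or 8.8 (30%/10%), an error of under half a point.

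**Step 4. What the binary term does achieve.** Take control with 15% missing in both grades.
- Observed successes are 0.85 × 0.7325 = 0.6226, and the missing share is 0.15 × 0.85 = 0.1275.
- With the term, missing patients get 0.7325/0.85 = 86.2%, and the arm rate is 0.6226 + 0.1275 × 0.862 = 73.25%, which is correct.
- Without the term, they get 0.6226/(0.7225 + 0.15) = 71.4%, and the arm rate falls to 71.4%, about 1.9 points low.

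**The case against.** The strongest reply is that this is a refinement of a reasonable model. The SAP prespecifies imputation within arm, with both patient-level strata used in the analysis model, aneurysm size and an interim outcome. Both arms follow the same imaging schedule, and with a shared pattern of return the contrast hardly moves. That stands, and it limits the weight of the point.

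Stronger readings are tempting, and the documents do not support them:
- A reader might infer that the term is useless because it is constant. It is not: it keeps early failures out of the donor rate (step 4), and it varies for patients without a readable 3-6 month scan.
- A reader might infer that the treatment effect is biased by 2 points or more. That needs threefold dependence on grade running in opposite directions in the two arms. Unblinded care makes this possible; nothing in the documents makes it likely.
- A reader might infer that the SAP confirms binary coding. It only implies it.
- A reader might infer that the imputation breaks down because inadequate at 3-6 months predicts failure perfectly. An ordinary logistic step has no finite coefficient there and the SAP names no safeguard. But no patient with an observed reading in that category needs imputation, and SAP 6.1 allows a better method if the SAP is updated before lock.

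A simpler remedy also fails: a grade 1 against 2 predictor with early failures dropped altogether. A patient missing both scans could then never be imputed as an early failure. On the step 3 inputs such patients would be imputed at 73.25/85 = 86.2% instead of 73.25% in control, and at 80/90 = 88.9% instead of 80% in the larger-coil arm. If 10% missed both scans at random (assumed), arm rates would rise by about 1.3 and 0.9 points and the contrast would fall by about 0.4, more than the 0.15 points at issue.

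**Conclusion.** The point holds in a limited form. On the natural binary reading, the only follow-up predictor cannot rank patients within the adequate group, although the core lab reads the grade that could.

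The cost is zero bias if return does not depend on grade. With 30%/10% missingness it is about 1 point per arm, and about 0.15 points in the contrast (under half a point on the second set of inputs) when the arms behave alike. Opposite strong patterns by arm bring it to about 2.3 of 6.75 points. All of these sizes rest on assumed grade mixes, later adequacy and missingness, and leave out what the baseline covariates might absorb.

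This is an improvement worth making because it is nearly free and makes missing at random more credible. It does not show that the planned primary test is invalid.

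**What to change.** In SAP 6.5.3, replace the 3-6 month occlusion status with the core-lab Raymond grade at that visit, kept at three levels (1, 2, 3), and add an ordinal type to the list of variables. Then state the order of imputation, within arm:

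1. For a patient with no readable 3-6 month scan and a missing endpoint, impute the 3-6 month grade first, with early failures kept as donors for this step.
2. Set an imputed grade 3 to failure, as SAP 5.1 requires.
3. For an observed or imputed grade 1 or 2, impute 12-18 month occlusion from patients with no earlier Raymond score above 2, with grade 1 against 2 as a predictor. This also removes the perfectly predicted category from the outcome regression.
4. A patient who lacks only the 3-6 month scan keeps the outcome given by the observed scans.

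If the grade was intended all along, the same wording settles it. The cost is sparser cells and slightly more modelling. No new data are needed, and the SAP's purpose section allows revision before data lock.

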A major focus of clinical research has been improving aneurysm occlusion and recurrence rates through modification of techniques, devices and embolic materials. Until recently, bare platinum detachable coils, which are biologically inert, had been the mainstay for neuro-interventionists. The first bioactive coil approved by the U.S. Food and Drug Administration, the Matrix coil (Stryker), has only modest evidence supporting its use. More recent bioactive and non-bioactive coils, including hydrogel and Cerecyte coils, have more robust evidence supporting their use. Both types of coil have recently completed evaluation in large, prospective randomized trials. Promisingly, the unpublished data suggests excellent aneurysm occlusion rates; however, the primary endpoints of both studies were not statistically different compared to bare platinum coils. Although it is apparent that occlusion rates have improved since the initial ISAT data, new coil designs have yet to demonstrate superiority over bare platinum coils in a randomized controlled trial.

Considerable emphasis has been placed on the volumetric filling of aneurysms, or ‘packing density’, which has been related to long-term outcome. Packing density of 20-30% has been suggested as being the desired packing to ensure stable occlusion, however achievement of densities exceeding 25% can be difficult in aneurysms larger than 5mm. The use of framing coils, or large-diameter coils initially placed into the aneurysm to serve as a foundation for the placement of smaller-diameter “filling” coils, has demonstrated efficacy in

case series. Framing platinum coils of larger diameter are resistant to deformation regardless of flow rate in a flow-model, unlike smaller-diameter framing coils which became unstable as flow rate increases. These studies suggest that larger diameter platinum coils may be more stable during and after endovascular aneurysm coil embolization, and that smaller-diameter framing coils may have a higher propensity towards recanalization. It should be noted that, contrary to the name, current “Eighteen” platinum coils produced by Stryker (Natick, MA) are actually 0.014-0.0155 inches in size. These coils are larger than standard coils, which are usually sized 0.010 or 0.012”.

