## **3. Objectives**

### **3.1 Primary Outcome**

Occlusion rate: Angiographic occlusion, improvement or no change in the post-coiling appearance of the aneurysm as judged by an independent core lab on follow-up angiography at 12-18 months after endovascular embolization.

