### 6.2 Assessments

#### 6.2.1 Angiographic assessment

1. Procedural angiograms (as part of standard of care) will be collected at enrollment and follow-up. Follow-up angiograms should be performed at 3-6 months and again at 12-18 months post-coiling. De-identified JPEG files of the imaging will then be uploaded into the electronic data-capture system and sent to the core lab for evaluation and subsequent analysis. Images should show measurements or a dime should be placed for scale.

2. An independent core lab, not affiliated with Vanderbilt University Medical Center, will review and analyze all uploaded images. The core lab, using standard criteria and being blinded to treatment arm will confirm (1) aneurysm size/volume and dome to neck ratio, and (2) degree of occlusion at the end of treatment and on follow-up imaging. Digital subtraction angiography (DSA) or MRA are required for the 3-6 month and 12-18 months follow-up angiogram.

3. Volumetric filling will be determined by the core lab based on measurements of the aneurysms relative to dimes, and of the coils used provided by participating centers on the procedure case report form.

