## **9. Statistical Methods**

### ***9.1 Sample Size Estimate and Power of the Study***

Based upon a presumed absolute improvement in recanalization rate (defined as an increase in Raymond Scale from immediate to 12-18 month follow-up, as determined by the core laboratory analysis) of 9% (73% recanalization rate for non-Eighteen versus 82% for Eighteen) with an Alpha 0.05 and Power = 80, 325 patients would be required for each arm (at least 650 total patients).

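### The primary imputation model omits the end-of-procedure Raymond grade and, for patients missing both follow-up scans, does not tie a drawn 3-6 month failure to the endpoint

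*Combined protocol and SAP*

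**What the plan says.** SAP 6.5.3 runs multiple imputation by fully conditional specification, separately by randomized arm, assuming data are missing at random, with 30 datasets. The models use age, sex, the rupture and neck strata, "aneurysm size, and angiographic occlusion status at the 3 to 6 month visit". The list has no open-ended term, and the immediate post-coiling result is not on it.

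That result is available. Under protocol 6.2.1 the blinded core lab confirms "degree of occlusion at the end of treatment and on follow-up imaging". The protocol also treats it as the reference point for durability. Section 3.1 counts as success "improvement or no change in the post-coiling appearance of the aneurysm", and section 9.1 defines recanalization as an "increase in Raymond Scale from immediate to 12-18 month follow-up". Packing density is a planned secondary endpoint, and the protocol background describes it as a quantity "which has been related to long-term outcome".

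SAP 5.1 sets the endpoint rule: "If any of these angiograms show inadequate angiographic occlusion (Raymond score >2), the patient will be considered to have inadequate occlusion" and is a treatment failure. SAP 6.5.3 restricts missing status to patients with no earlier evidence of inadequate occlusion. It states no rule linking a drawn 3-6 month value to a drawn endpoint, and no method for handling separation.

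**The concern.** **Omitted grade.** Whether a patient returns for imaging may depend on how well the aneurysm was occluded at treatment. If it does, missing-at-random holds only when that grade is in the model. For a patient with a 3-6 month scan, that scan carries much of the information. For a patient with neither scan, the model knows the aneurysm's starting geometry but nothing about what coiling achieved. The other analyses of the primary endpoint planned in the SAP concern center (6.5.4), chance imbalance (6.5.5) and subgroups (6.5.6), so none would reveal a bias from this source.

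**Consistency.** A patient missing both scans needs the 3-6 month status drawn as well as the endpoint. In the observed data an inadequate 3-6 month scan always means endpoint failure, by definition. A logistic model for the endpoint therefore has a perfectly predictive term (quasi-complete separation). Coefficient draws from such a fit can be erratic, and a completed record may hold a 3-6 month failure together with an endpoint success, a combination the endpoint definition does not allow.

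**Working it through.** **The plan's own figure.** SAP 6.5.2 gives 73% vs 82%, 325 per arm, two-sided 0.05. With mean rate 0.775, power = Φ[(0.09·√325 − 1.96·√(2·0.775·0.225)) / √(0.73·0.27 + 0.82·0.18)] = Φ[(1.6225 − 1.1575)/0.5871] = 78.6%. This fits the stated approximately 80%. The 9-point effect is the yardstick for what follows; the concern does not alter the sample size.

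**Omitted grade, by expected values.** The documents give no missingness rate and no grade distribution, so these are assumptions: success 90/76/38% for immediate Raymond 1/2/3; grade mix 45/35/20%; no true effect. If grade is ignored, missing patients are in effect given the observed-case rate.

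- True rate: 0.45·0.90 + 0.35·0.76 + 0.20·0.38 = 74.70%.
- Missing 10/12/20% by grade (12.7% overall): observed rate 0.65938/0.8730 = 75.53%, bias +0.83 points.
- Missing 15/12/6% by grade (12.15% overall): observed rate 0.64977/0.8785 = 73.96%, bias −0.74 points.
- One pattern in each arm: false difference 0.83 + 0.74 = 1.57 points.

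With a 45/40/15% mix (true rate 76.60%) the two biases are +0.67 and −0.60, a difference of 1.27. Other plausible mixes gave 1.2-1.6.

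Now put the same 10/12/20% pattern in both arms. With identical grade mixes the biases cancel. With 45/35/20% in one arm and 45/40/15% in the other they are +0.83 and +0.67, leaving about 0.2 points. The range under this kind of assumption was 0.2-0.4.

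**Omitted grade, by simulation.** Fully conditional logistic imputation within arm; 325 per arm; 60 trials per scenario; 5 imputations. Assumed: 10-15% missing both scans; 5-10% missing only the later one; 60% of failures visible at 3-6 months; grade mix 45/40/15%; missingness 2.5 times higher in grade 3. Separation was handled by data augmentation and no consistency rule was applied.

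| Missing both / later only | Bias without grade (control, larger) | Bias with grade (control, larger) |
|---|---|---|
| 10% / 10% | +0.49, +0.65 | −0.38, −0.63 |
| 15% / 5% | +0.84, +0.87 | −0.50, −0.36 |

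Standard errors are 0.14-0.17 points. Without the grade the arms differ by only 0.16 and 0.03 points. The negative remainder with the grade is not evidence against adding it: when missingness was unrelated to grade, the same procedure with the grade already gave −0.18 to −0.65. A separate simulation found the per-arm bias falling from about 0.7-0.9 points to about 0.

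**Consistency.** In the same simulation, contradictory records arose only in patients missing both scans.

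| Handling | Endpoint success among records with a drawn 3-6 month failure | Contradictory records as share of all imputed endpoints |
|---|---|---|
| Separation unhandled | 43-47% | 9-17% |
| Augmented data | about 4-5% | 0.2-0.8% |
| Augmented data plus rule that drawn failure means endpoint failure | 0 | 0 |

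The net effect does not follow from these shares. A one-step calculation (10% missing both × 12% inadequate at 3-6 months × 0.50 drawn as success) suggests 0.6 points too much success. The full procedure also draws spurious 3-6 month failures. With separation unhandled it gave success rates that were too low: control by 0.2-0.7 points, larger-coil by 0.8-1.7. A further simulation gave −1.2 points (SE 0.13) unhandled and −0.03 (SE 0.07) with augmentation.

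**The case against.** A reader might infer that the model can turn known failures into successes. It cannot. SAP 5.1 makes an observed Raymond score above 2 a failure, and SAP 6.5.3 keeps such patients out of the missing set. Only patients with neither scan are affected.

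A reader might also infer a 1.6-point false difference, or a 0.6-point overstatement of success from separation. The first needs grade-dependent missingness running in opposite directions by arm. Operators are unblinded, so this is conceivable, but nothing in the documents supports it. The second ignores that the procedure also draws the 3-6 month status, and the full simulations gave the opposite sign.

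Other objections stand in part:

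- The model already includes aneurysm size and neck stratum. The protocol links size to occlusion and the neck and rupture strata to ease of dense packing, so missing patients are not imputed blind. These remain baseline determinants and do not record the result achieved.
- SAP 6.5.3 does not prescribe unpenalised logistic draws, and SAP 6.1 allows unsuitable methods to be replaced before lock. Separation handling is therefore unspecified rather than wrong. For a primary analysis it is still better specified in advance.
- Packing density has its own gaps, and SAP 6.6.5 says they will not be imputed. That is a fair reason not to require it as an imputation variable.
- The grade is measured after randomization. This does not bar it: it would be an auxiliary variable in arm-specific imputation models, and the analysis model in SAP 6.5.1 stays as it is.

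**Conclusion.** The concern holds in limited form. The model leaves out a collected, directly relevant variable, and patients missing both scans are imputed without any information on the treatment result. Under the assumed missingness each arm's rate is off by roughly 0.5-0.9 points. The effect on the comparison is about 0.2-0.4 points if missingness follows the same pattern in both arms, and 1.2-1.6 points only under opposite patterns. Against a 9-point design effect this is unlikely to decide the trial, but it is avoidable.

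The consistency gap is real and narrow. Its size ranges from negligible to material according to a software choice that the SAP leaves open, and the direction of its effect on the treatment comparison is not established. All magnitudes rest on assumed missingness rates, grade mixes and success rates, because the documents give none of these.

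**What to change.** Amend SAP 6.5.3 as follows:

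1. Add the core-lab end-of-procedure Raymond grade to the arm-stratified imputation model, and impute the grade itself where absent, for example when coiling was not started.
2. Impute 3-6 month status first. Where the endpoint is missing and the drawn 3-6 month status is inadequate, set the endpoint to failure.
3. Fit the 12-18 month imputation only among patients adequate at 3-6 months, using augmented or penalised logistic regression, and name the method.
4. Optionally add packing density as a further auxiliary variable, if the plan says how its missing values are handled.

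The cost is SAP wording and programming. The grade is already read by the core lab, no new data are needed, and the analysis model and sample size do not change. The SAP's purpose statement permits revision before data lock.
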